7.10 Duration of Follow Up

Patients will be followed for 6 months after removal from study or until death, whichever occurs first. Patients removed from study for unacceptable adverse events will be followed until resolution or stabilization of the adverse event.

7.10 Measures to Minimize Bias: Randomization and Blinding

N/A. This study is an open label single arm (non-randomized) study

7.12 Study Intervention/Follow-up Compliance

Subject compliance with the dosing schedule will be entered on a drug diary that the subject will complete and return to the site for review. A participant will be considered lost to follow-up if he or she fails to return for scheduled visits and is unable to be contacted by the study site staff (see section 8.3)

8. Study Intervention Discontinuation and Participant Discontinuation/Withdrawal

See section 7.9

8.1.1 Discontinuation of Study Intervention

8.1.1. Tier 1 Stopping Rule:

The primary objective of Tier 1 is to assess the feasibility of protocol therapy in subjects with advanced MPNs as measured by the incidence of dose limiting toxicity (DLT, see *Definition of Dose Limiting Toxicity* section). Toxicities are assessed by CTCAEv5 criteria. Up to a total of 12 patients will be accrued to Tier 1. Tier 1 will be stopped for safety considerations under the following conditions:

- Any patient has grade 5 (lethal) DLT occurring within the first 12 weeks of starting vactosertib; or
- More than two patients experience a dose-limiting toxicity (DLT) at any dose, within the first 12 weeks on study.

Trial accrual will be suspended and a DSMB convened if either of these *Tier 1 Stopping Rule* criterion is triggered. If more than two patients have a DLT at the same dose level, then further accrual to that dose level and higher dose levels will be suspended. Pending review with DSMB, the study may be re-opened with amendment reflecting changes to the permitted dose levels. A planned stop to Tier 1 accrual will occur after 12 subjects have received at least one dose of vactosertib. At this time, the DSMB will be convened if fewer than 1 of the first 12 patients experience clinical benefit.

Protocol therapy will be considered safe if the *Tier 1 Stopping Rule* is not triggered. The following table provides the marginal probability of declaring the intervention unsafe for different rates of severe toxicity (as defined by *Tier 2 Stopping Rule*). This *Tier 1 Stopping Rule* protects against an unexpectedly high rate of severe toxicity.

Tier 1	True Rate of Severe Toxicity				
	5%	10%	15%	20%	30%
Probability of Declaring Unsafe	12%	35%	56%	73%	91%

If the Tier 1 safety boundaries are not crossed, this treatment strategy will be considered safe for expansion to Tier 2. Feasibility and toxicity will continue to be monitored in the Tier 2 portion of the study. A total of 37 patients will be accrued (Tier 1 + Tier 2) and the Tier 2 rule stopping rule applies to all subjects (up to 37) enrolled.

8.1.2. Tier 2 Stopping Rule:

- Any patient has grade 5 (lethal) DLT occurring within the first 12 weeks of starting vactosertib; or

- More than five patients experience a dose-limiting toxicity (DLT) at any dose, within the first 12 weeks on study.

Protocol therapy will be considered safe if the *Tier 2 Stopping Rule* is not triggered. The following table provides the marginal probability of declaring the intervention unsafe for different rates of severe toxicity (as defined by *Tier 2 Stopping Rule*). The *Tier 2 Stopping Rule* protects against an unexpectedly high rate of severe toxicity.

Tier 2	True Rate of Severe Toxicity				
	5%	10%	15%	20%	30%
Probability of Declaring Unsafe	3.1%	31%	67%	89%	99%

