After completion of planned study vactosertib treatment on either Tier, subjects meeting one of the following criteria will be provided the option of continuing vactosertib for up to 2 years or until such a time that they manifest disease progression or unacceptable toxicity:

- Subject meets *Criteria for Clinical Benefit* after completion of planned therapy on their study Tier of vactosertib, or
- Subject has not experienced a dose limiting toxicity (DLT) from vactosertib and has maintained at least stable disease after completion of planned therapy on their study Tier as per IWG-MRT/ELN Response Criteria.

7. Study Intervention

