12.5 Interim Analysis

Reports of toxicity and efficacy will be submitted for DSMB review at the following time points:

- completion of Tier1;
- completion of Tier2;
- any time one of the stopping rules is met.

Unscheduled Interim Analysis will be performed if more than three patients have a DLT at the same dose level or if more than five patients in both tiers, at any dose level, have a DLT. In the former situation, further accrual to that dose level and higher dose levels will be suspended. In the latter situation, further accrual to the study will be halted. Reports of toxicity and efficacy will be submitted for DSMB review in that instance for review and guidance as to whether the dose level can be re-opened or accrual to the study can proceed and if the study should be amended to permanently close the problematic dose levels or closed altogether.

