The principal investigator will be primarily responsible for monitoring the safety of the study, adverse events, both serious and non-serious and deaths that occur during study participation by subjects. All adverse events will be monitored until they resolve or are clearly determined to be due to a subject's disease or intercurrent illness(es).

At the completion of Tier 1, all data necessary to evaluate [Criteria for Decision to Proceed to Tier 2](#) section) will be reported to WCM Statistician, WCM DSMB and Medpacto. The Simon Two-stage

Optimum Design is expected to minimize the number of subjects exposed to vactosertib if it is found to be an unsuitable agent for the treatment of anemic patients with Ph-neg MPNs. If 1 or more subjects meets the endpoint then the study will proceed to Tier 2 and another 25 subjects will be enrolled). This decision will be submitted to WCM IRB at the time of continuing review.

After completion of Tier 2, all data necessary to evaluate will be reported to WCM Statistician, WCM DSMB and Medpacto. If four or more subjects meet the Composite Response & Toxicity Endpoint then vactosertib will have shown preliminary efficacy and feasibility to justify further evaluation as an agent to treat anemic patients with Ph-Neg MPNs. This interpretation will be submitted to WCM IRB at the time of continuing review.

Should the Stopping Rules for [Tier 1](#) or for [Tier 2](#) be met, accrual of new subjects will be immediately suspended and the WCM IRB and Medpacto will be notified. The study DSMB will meet to review study data. The DSMB may either recommend permanent closure of the study or may allow protocol revision/amendment and submission to WCM IRB for review. DSMB recommendations will be submitted to Medpacto and WCM IRB.

All protocol amendments and consent form modifications will be made by the Principal Investigator. Medpacto will have the opportunity to review and approve the changes prior to submission of these changes to the local IRB.

[Section 7.9, Criteria for Removal from Study](#), details treatment stopping rules for individual patients.

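### The lethal-DLT trigger ends at week 12 of 16 or 24 planned weeks; a single later lethal DLT that crosses no DLT count reaches the DSMB only in the tier-completion report

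*Combined protocol and SAP*

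**What the plan says.** Sections 8.1.1 (Tier 1) and 8.1.2 (Tier 2) share the same lethal limb: "Any patient has grade 5 (lethal) DLT occurring within the first 12 weeks of starting vactosertib". Their count limbs, more than two patients in Tier 1 and more than five across all 37, use the same 12 weeks.

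Treatment runs longer. Section 7.9.1 plans 16 weeks in Tier 1 and 24 in Tier 2. Under 6.3.7, patients who benefit, or who are stable without a DLT, "will be provided the option of continuing vactosertib for up to 2 years". The DLT definition in section 13 has no time limit and includes a death from any adverse event whatever its cause.

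The routes to the DSMB are these:
- Section 15: when an 8.1 rule is met, "accrual of new subjects will be immediately suspended and the WCM IRB and Medpacto will be notified", and the DSMB meets.
- Section 12.5: reports at completion of Tier 1, at completion of Tier 2, and "any time one of the stopping rules is met".
- Section 12.5, unscheduled: more than three patients with a DLT at one dose level, or "if more than five patients in both tiers, at any dose level, have a DLT". For the second, "In the latter situation, further accrual to the study will be halted".
- Section 8.1.1: more than two patients with a DLT at one dose level suspends that level and those above it, pending DSMB review.

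On the conclusion drawn, 8.1.1 states: "If the Tier 1 safety boundaries are not crossed, this treatment strategy will be considered safe for expansion to Tier 2". Section 8.1.2 states: "Protocol therapy will be considered safe if the *Tier 2 Stopping Rule* is not triggered".

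**The concern.** The plan treats one lethal DLT in week 11 as enough to suspend accrual and convene the DSMB. The same event in week 13, in a patient still on the drug, does neither by itself, and no reason is given for the difference. In Tier 2 half of each patient's planned treatment lies after the cut-off. Enrolment could therefore continue after an on-treatment death without the independent board having been asked to weigh it.

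There is also a question of consistency. The 8.1 rules state a 12-week window and 12.5 states none. If 12.5 counts later DLTs, accrual could be halted under 12.5 while the 12-week rule in 8.1.2, being untriggered, still supports a conclusion that therapy is safe.

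**Working it through.** The plan gives no figure for events after week 12, so there is none to reproduce. Its tables of the probability of declaring therapy unsafe concern the DLT counts and are not used here.

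**1. Exposure outside the window** (12 and 25 patients; 16 and 24 weeks)
- Planned: 12×16 + 25×24 = 792 patient-weeks.
- Inside the window: 37×12 = 444.
- Outside: 792 − 444 = 348, and 348/792 = 43.9%.
- By tier: 4/16 = 25% in Tier 1 and 12/24 = 50% in Tier 2.

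**2. What happens to one lethal DLT after week 12 that crosses no count**

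| Route | Prompt DSMB review or accrual pause? |
|---|---|
| 8.1.1, 8.1.2 lethal limb | No, outside the window |
| Section 15 | No, depends on the 8.1 rules |
| 12.5, stopping rule met | No |
| 12.5 counts | No, although the event adds one to them if they have no window |
| 12.5, tier completion | Reaches the DSMB then |
| SAE reports (13.2.1 to 13.2.3) | IRB, FDA and supplier; DSMB not named |
| Unanticipated-problem reports (14.1.2) | IRB and coordinating centre/sponsor within 24 hours, if it qualifies; DSMB not named |

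**3. Delay to the Tier 2 completion report** (2 patients per month, section 12.2)

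Assumptions: even entry without interruption, full treatment, and events spread evenly over weeks 12 to 24. Continuation under 6.3.7 is left out.
- Entry of patient k is at (k − 1)×52/24 weeks. The last entry is at week 52 and completion at 52 + 24 = 76.
- Mean event time is 26 (mean entry) + 18 (mean of 12 to 24) = 44. Mean delay is 76 − 44 = 32 weeks.
- Range: 76 − 12 = 64 weeks down to 0.
- Share of late exposure before week 52: the first 13 patients contribute all of theirs. The next six contribute (40 − entry)/12 each, summing to 3.21. (13 + 3.21)/25 = 65%. Over that time a mean of 8.7 patients (range 1 to 19) are still to be enrolled.

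**4. How often (assumptions only)**

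The documents give neither DLT timing nor the lethal share. Assume a 10% DLT rate in 12 weeks, so a weekly hazard h = −ln(0.9)/12, falling to r×h after week 12, and a lethal share f. The table shows the chance that a Tier 2 late lethal DLT occurs before any 8.1 rule or the 12.5 total count is met. It comes from simulation, 200,000 trials per cell.

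| | r = 0 | 0.25 | 0.5 | 1 |
|---|---|---|---|---|
| f = 10% | 0% | 3.4% | 6.1% | 9.6% |
| f = 20% | 0% | 5.4% | 9.5% | 15.1% |

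These are upper values, because the same-dose-level rules are not modelled. If every DLT fell at one dose level, the entries for r = 0.25, 0.5 and 1 would drop to about 2.0, 3.3 and 4.7% (f = 10%) and 3.5, 5.6 and 8.1% (f = 20%).

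**5. The 12.5 count against the conclusion in 8.1.2**

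If 12.5 has no window, the chance that its count exceeds five while 8.1.2 is untriggered is the sum over early counts w ≤ 5 of P(w)×(1 − f)^w×P(late DLTs ≥ 6 − w). At the 10% rate, for r = 0, 0.25, 0.5 and 1:
- f = 0: 0, 11.0, 23.2, 46.4%.
- f = 10%: 0, 6.8, 14.9, 31.5%.
- f = 20%: 0, 4.0, 9.2, 20.7%.

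If 12.5 shares the 12-week window, all of these are zero.

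**The case against.** A reader might infer that a late death never reaches the DSMB. The documents do not support that: 12.5 sends toxicity reports at completion of each tier. For a Tier 1 death in weeks 13 to 16, the completion report comes before expansion. The weakness is one of timing, and it falls mainly in Tier 2.

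A reader might also infer that the plan contradicts itself by calling therapy safe after halting accrual. That requires 12.5 to be read as having no window. Its count of more than five across both tiers matches 8.1.2 in threshold, population and dose wording, and may simply restate it. Even on the other reading, the DSMB is already reviewing the trial once the count is met. Nothing after Tier 2 depends on the sentence in 8.1.2: further development rests on the composite endpoint (12.1.1, Table 5), which excludes any patient with a DLT and sets no time limit. The percentages in step 5 therefore measure a possible wording mismatch and not patient risk.

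Other oversight is real. The principal investigator monitors deaths, fatal suspected reactions go to FDA within 7 days, and unanticipated-problem reports are due in 24 hours and must describe corrective actions. These limit the seriousness of the gap. They do not give the DSMB a prompt look before more patients enter.

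The frequencies in step 4 also assume full treatment, although 6.3.3 and 7.9 remove patients for several reasons.

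**Conclusion.** The gap is real and worth closing. On the text alone, the lethal trigger leaves out 44% of planned exposure and half of Tier 2. A single later lethal DLT that crosses no count waits for the tier-completion report. The Tier 2 delay of about 32 weeks (0 to 64), with about 65% of late exposure before the last entry, rests on the stated accrual rate and the assumptions in step 3.

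The chance that it happens is not established: it runs from zero upward with the assumed late hazard and lethal share. The possible conflict between 12.5 and 8.1.2 is a secondary point of consistency.

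**What to change.** Keep the 12-week counts and thresholds in 8.1.

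1. Add to 12.5 and section 15 that any lethal DLT after week 12 while on vactosertib, including continuation under 6.3.7, is reported promptly to the DSMB (for example within 24 hours, as in 14.1.2), and that the DSMB decides whether accrual is suspended.
2. State in 12.5 whether its counts include DLTs after week 12. If they do, limit the safety conclusions in 8.1.1 and 8.1.2 to the first 12 weeks and make them conditional on 12.5 not having been triggered.

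This costs a few sentences, with no new visits, thresholds or tables. The downside is an occasional extra DSMB review, sometimes for a death unrelated to the drug, because the DLT definition ignores attribution.

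Expected extra reviews, assuming a 10% 12-week DLT rate with 10% lethal:
- Planned treatment only: 0 at r = 0. At r = 1, the late lethal risk is 0.1×0.9×(1 − 0.9^(4/12)) = 0.0031 per Tier 1 patient and 0.1×0.9×(1 − 0.9) = 0.009 per Tier 2 patient, giving 12×0.0031 + 25×0.009 = 0.26.
- With continuation for 2 years (104 more weeks) and r from 0.25 to 1: about 0.4 to 1.2 if half of patients continue, and 0.7 to 2.1 if all do.

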Back pain	2 (6)	0 (0)	2 (4)
Hyponatraemia	2 (6)	0 (0)	2 (4)
Acidosis	1 (3)	0 (0)	1 (2)
Alanine aminotransferase increased	1 (3)	0 (0)	1 (2)
Arthritis	0 (0)	1 (12)	1 (2)
Aspartate aminotransferase increased	1 (3)	0 (0)	1 (2)
Asthma	0 (0)	1 (12)	1 (2)

Blood bilirubin increased	1 (3)	0 (0)	1 (2)
Cerebrovascular accident	1 (3)	0 (0)	1 (2)
Convulsion	1 (3)	0 (0)	1 (2)
Dehydration	1 (3)	0 (0)	1 (2)
Dyspnoea	1 (3)	0 (0)	1 (2)
Gastrointestinal haemorrhage	1 (3)	0 (0)	1 (2)
Headache	1 (3)	0 (0)	1 (2)
Hemiparesis	1 (3)	0 (0)	1 (2)
Hypokalaemia	1 (3)	0 (0)	1 (2)
Hypophosphataemia	0 (0)	1 (12)	1 (2)
Nausea	1 (3)	0 (0)	1 (2)
Pleural effusion	1 (3)	0 (0)	1 (2)
Pulmonary oedema	1 (3)	0 (0)	1 (2)
Pyelonephritis	1 (3)	0 (0)	1 (2)
Sepsis	1 (3)	0 (0)	1 (2)
Sinus tachycardia	1 (3)	0 (0)	1 (2)
Small intestinal obstruction	1 (3)	0 (0)	1 (2)
Stridor	1 (3)	0 (0)	1 (2)
Tumour pain	1 (3)	0 (0)	1 (2)
Upper gastrointestinal haemorrhage	0 (0)	1 (12)	1 (2)
Vomiting	1 (3)	0 (0)	1 (2)
Weight decreased	1 (3)	0 (0)	1 (2)

No subjects experienced Grade 3 or 4 AEs in MP-VAC-105 study. And three grade 5 events were reported from vactosertib monotherapy trials; disease progression (MP-001), gastric ulcer perforation (MP-001), and metastatic ovarian cancer (MP-001), none of which were causally related with vactosertib.

Listed below are the adverse events that were deemed related to, or from which one could not exclude the possibility of its relationship with vactosertib, as determined by MedPacto. For the purpose of determining regulatory authority reportability, when assessing expectedness, listed below are the adverse events that are considered to be expected (Table X).

Table 8 List of adverse events of Vactosertib that can be considered expected

System Organ Class (MedDRA SOC)	Adverse Event (MedDRA PT)
Gastrointestinal disorders	Constipation
	Diarrhoea
	Dyspepsia
	Nausea
	Vomiting

Immune system disorders ¹⁾	Asthma
	Interstitial lung disease
Renal and urinary disorder	Tubulointerstitial nephritis
Respiratory, thoracic and mediastinal disorders	Lung infiltration ²⁾ – not related, as a descriptive term rather than diagnostic. However, it can be considered as related when there is underlying immune mechanism involved.
General disorders and administration site conditions	Fatigue
Investigations	Alanine aminotransferase increased
	Aspartate aminotransferase increased
Nervous system disorders	Headache
Skin and subcutaneous tissue disorders	Rash ³⁾
	Pruritus

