Table 11: Adverse drug reaction (≥3%) from vactosertib monotherapy

AE Terms	MP-001 (n=35), n (%)	MP-VAC-105 (n=16), n (%)	MP-MDS-01 (n=9), n (%)	Total (n=60), n (%)
Headache	5 (15)	5 (32)	1 (12)	11 (19)
Fatigue	10 (29)	0 (0)	1 (12)	11 (19)
Nausea	9 (26)	1 (7)	0 (0)	10 (17)
Diarrhoea	5 (15)	1 (7)	1 (12)	7 (12)
Decreased appetite	6 (18)	0 (0)	0 (0)	6 (10)

Vomiting	5 (15)	0 (0)	0 (0)	5 (9)
Hypophosphataemia	3 (9)	0 (0)	1 (12)	4 (7)
Constipation	4 (12)	0 (0)	0 (0)	4 (7)
Dermatitis acneiform	2 (6)	0 (0)	1 (12)	3 (5)
Aspartate aminotransferase increased	3 (9)	0 (0)	0 (0)	3 (5)
Pruritus	3 (9)	0 (0)	0 (0)	3 (5)
Abdominal pain	2 (6)	0 (0)	0 (0)	2 (4)
Alanine aminotransferase increased	2 (6)	0 (0)	0 (0)	2 (4)
Amylase increased	2 (6)	0 (0)	0 (0)	2 (4)
Anaemia	2 (6)	0 (0)	0 (0)	2 (4)
Blood alkaline phosphatase increased	2 (6)	0 (0)	0 (0)	2 (4)
Dysgeusia	2 (6)	0 (0)	0 (0)	2 (4)
Dyspepsia	2 (6)	0 (0)	0 (0)	2 (4)
Lipase increased	2 (6)	0 (0)	0 (0)	2 (4)
Muscular weakness	2 (6)	0 (0)	0 (0)	2 (4)
Pyrexia	2 (6)	0 (0)	0 (0)	2 (4)
Rash maculo-papular	2 (6)	0 (0)	0 (0)	2 (4)

- Vactosertib may increase immunologic toxicities of when administered in combination with anti-cancer PD1/PD-L1 pathway inhibitors.

Dose Limiting Toxicity.

- Dose limiting toxicity is defined as any of the following: Any occurrence of death as result of adverse event regardless of attribution;
- Any non-hematologic grade ≥ 3 toxicity (CTCAEv5 criteria), except for nausea, vomiting or diarrhea lasting 3 days or less;
- Any grade 4 neutropenia (CTCAEv5 criteria) of any duration;
- Any grade ≥ 3 neutropenia that has not recovered to grade ≤ 2 within 7 days of onset;
- Any grade ≥ 3 febrile neutropenia (temperature \geq);
- Any grade ≥ 3 thrombocytopenia associated with clinically significant bleeding; or requiring platelet transfusion.

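### The printed Tier 1 and Tier 2 probabilities of declaring vactosertib unsafe do not belong to the stopping rules as worded; the Tier 1 figures overstate protection by 8 to 30 points at 10–30% toxicity

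*Combined protocol and SAP*

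**What the plan says.** Section 8.1.1 stops Tier 1, which has up to 12 patients, on either of two events. One is "Any patient has grade 5 (lethal) DLT occurring within the first 12 weeks of starting vactosertib". The other is "More than two patients experience a dose-limiting toxicity (DLT) at any dose, within the first 12 weeks on study". Section 8.1.2 keeps the lethal trigger and changes the count: "More than five patients experience a dose-limiting toxicity (DLT) at any dose, within the first 12 weeks on study". Section 8.1.1 applies the Tier 2 rule to everyone enrolled, up to 37. Section 12.5 repeats the same count: "if more than five patients in both tiers, at any dose level, have a DLT".

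Each rule has a table introduced by this statement: "The following table provides the marginal probability of declaring the intervention unsafe for different rates of severe toxicity". For true rates of 5/10/15/20/30%, the Tier 1 table prints 12/35/56/73/91% and the Tier 2 table 3.1/31/67/89/99%. No formula, lethal rate or other assumption is given.

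The Tier 1 rule is also the safety gate: "If the Tier 1 safety boundaries are not crossed, this treatment strategy will be considered safe for expansion to Tier 2".

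**The concern.** More than two means three or more, and more than five means six or more. A rule needing three DLTs among 12 patients cannot fire 35% of the time when each patient has a 10% risk, unless something else contributes heavily. The only other contributor in the rule is the lethal trigger.

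These tables are the plan's only statement of how well the rules detect excess toxicity, and a rule that is not triggered is the plan's definition of safe. Section 13.1.1 says there are no vactosertib data in advanced MPN, so an IRB or DSMB judging the gate has little else to go on. There is also an operational ambiguity: at the second Tier 1 DLT the text says continue, while the table fits a rule that stops.

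**Working it through.** **Inputs.** Tier 1 n = 12 and Tier 2 n = 37 (section 8.1.1); count boundaries of 3 or more and 6 or more (8.1.1, 8.1.2, 12.5); true rates p and printed probabilities from the two tables. Severe toxicity is read as DLT, the event the rules count.

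**Formula, count only.** P(stop) = P(X ≥ k) = 1 − Σ over x < k of C(n,x) pˣ(1−p)ⁿ⁻ˣ. Checking after every patient gives the same answer, because a DLT count never falls.

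**Which boundary reproduces the print?** One DLT stricter than the text. For two or more of 12 at p = 20%: 1 − 0.8¹² − 12(0.2)(0.8¹¹) = 1 − 0.0687 − 0.2062 = 72.5%, printed 73%.

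**The rule as worded.** For three or more of 12 at p = 20%, also subtract 66(0.2²)(0.8¹⁰) = 0.2835: 1 − 0.5583 = 44.2%.

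**Formula with the lethal trigger.** If a share q of DLTs is lethal, P(stop) = 1 − Σ over x < k of C(n,x) pˣ(1−p)ⁿ⁻ˣ(1−q)ˣ. At p = 20%, q = 20%, k = 3: 1 − [0.0687 + 0.2062(0.8) + 0.2835(0.64)] = 58.5%. The documents give no lethal share, so q = 0–20% is an assumption.

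Tier 1 (%):

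| True DLT rate | 5% | 10% | 15% | 20% | 30% |
|---|---|---|---|---|---|
| Printed | 12 | 35 | 56 | 73 | 91 |
| 2 or more of 12 | 11.8 | 34.1 | 55.7 | 72.5 | 91.5 |
| 3 or more of 12 (as worded) | 2.0 | 11.1 | 26.4 | 44.2 | 74.7 |
| Printed minus as worded | 10.0 | 23.9 | 29.6 | 28.8 | 16.3 |
| As worded, q = 5% | 4.6 | 15.2 | 30.8 | 48.0 | 76.7 |
| As worded, q = 10% | 7.2 | 19.2 | 35.0 | 51.6 | 78.6 |
| As worded, q = 20% | 12.3 | 26.9 | 43.0 | 58.5 | 82.2 |
| Printed minus q = 20% | −0.3 | 8.1 | 13.0 | 14.5 | 8.8 |
| q needed to match print | 19 | 31 | 38 | 45 | 51 |

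Tier 2 (%), one look at all 37:

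| True DLT rate | 5% | 10% | 15% | 20% | 30% |
|---|---|---|---|---|---|
| Printed | 3.1 | 31 | 67 | 89 | 99 |
| 5 or more of 37 | 3.6 | 30.9 | 67.0 | 88.8 | 99.4 |
| 6 or more of 37 (as worded) | 1.0 | 16.0 | 48.7 | 77.8 | 98.3 |
| Printed minus as worded | 2.1 | 15.0 | 18.3 | 11.2 | 0.7 |
| As worded, q = 5% | 9.5 | 28.3 | 57.8 | 82.1 | 98.6 |
| As worded, q = 10% | 17.4 | 39.0 | 65.5 | 85.7 | 98.9 |
| As worded, q = 20% | 31.3 | 56.3 | 77.5 | 91.1 | 99.4 |
| q needed to match print | 1 | 6 | 11 | 16 | 11 |

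No single lethal share fits either row. The best one still misses a cell by 6.6 points in Tier 1 (q = 33%) and 7.9 points in Tier 2 (q = 6%).

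The stricter boundaries come within one point of all ten printed cells. Two of those cells differ by more than rounding: Tier 1 at 10% (34.1 against 35) and Tier 2 at 5% (3.6 against 3.1).

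**The case against.** The strongest defence is that the count-only figures are lower bounds, because one lethal DLT also stops the tier and section 13.1.1 counts as a DLT "Any occurrence of death as result of adverse event regardless of attribution". That is true. It raises the real stopping probability, but it cannot produce the printed rows: the share needed climbs from 19% to 51% across Tier 1. A constant lethal share is itself an assumption, since deaths from any cause need not scale with drug toxicity. Prior experience does not settle the value. Section 13.1.1 reports that "three grade 5 events were reported from vactosertib monotherapy trials", against 22 subjects with grade 3–4 events, all of any cause, so this gives scale only.

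The Tier 1 table says severe toxicity is defined by the Tier 2 rule. Reading that as the Tier 2 count applied to 12 patients gives at most 11.8% (at p = 30%), so it does not rescue the row.

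It is also fair that the wording is clear and consistent with section 12.5, so staff following the text would know what to do. A trigger suspends accrual for DSMB review; it does not close the study by itself. Other protections exist: the enrollment hold after three patients, dose holds, DSMB review when Tier 1 completes, and the requirement in section 12.1.1 for at least one responder without a DLT. These limit the harm. They do not make the stated probabilities correct.

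The Tier 2 part is weaker. The count-only gap is material only at 10–20% toxicity, and with the lethal trigger the printed row may be too low: at p = 10% and q = 20% the figure is 56.3% against 31% printed. The single look at 37 also leaves out the Tier 1 rule. Running both count rules in sequence gives 2.6/21.2/53.8/80.5/98.5%, which is not the printed row either.

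**Conclusion.** The concern holds. Neither table gives the probability of its worded rule. On count alone, Tier 1 print is 10 to 30 points too high across all five rates. With 0–20% of DLTs assumed lethal, it is 8 to 30 points too high at 10–30% toxicity. At a true DLT rate of 20% the table implies a 27% chance of passing Tier 1 (100 − 73). The worded rule gives 56% on count alone, and 42–52% with lethal shares of 20–5%.

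Tier 2 print is 11 to 18 points too high at 10–20% toxicity on count alone and close at 5% and 30%. Once the lethal trigger is included, the direction depends on the lethal share.

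The binomial results assume independent patients with a common DLT risk. That the tables were computed one DLT too strict is an inference from the close match; the documents do not say so.

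**What to change.** The sponsor and DSMB should decide which boundary was intended, then make rule and table agree in sections 8.1.1 and 8.1.2.

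- **Option A, stricter rule.** Change the counts to two or more (Tier 1) and five or more (Tier 2), align section 12.5, and correct the Tier 1 cell at 10% to 34% and the Tier 2 cell at 5% to 3.6%. The trial would stop more often.
- **Option B, keep the wording.** Print 2/11/26/44/75% for Tier 1 and 1/16/49/78/98% for Tier 2. Label both as the DLT-count criterion only, without the grade 5 trigger, and say that the Tier 2 row is a single look at 37 that leaves out the Tier 1 rule. No extra patients are needed.

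Because sections 8.1.2 and 12.5 agree on the Tier 2 count, the tables may be the likelier error, but the choice is a safety judgement.

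Under either option, add a row per tier that includes the grade 5 trigger over a stated range of lethal shares.

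A separate minor point for the same amendment: the per-dose-level suspension threshold is more than two patients in section 8.1.1 and more than three in section 12.5. State one threshold, or say where each applies.
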